# 6.4.3.2 Items to Be Performed During the Treatment Period (Day 1 to Day 84) and Follow-Up Period (Day 85 to Day 162)

The visit window for items performed on Day 8 to Day 92 is  $\pm 2$  days, and the visit window for items performed on Day 106, Day 134, and Day 162 is  $\pm 7$  days.

- Administration status of the study drug Whether the study drug was administered, date/time of study drug administration, dose level, actual dose (mg)
- 2) Investigating concomitant medications and concomitant therapy
- 3) Investigating adverse events
- 4) Body weight
  - <Observation point>
  - Day 29, Day 57, Day 85
- 5) Vital signs and clinical findings
  - <Observation point>
  - Day 1 (pre-dose and 1 hour, 2 hours, and 6 hours post-dose), Day 2, Day 8, Day 15, Day 22, Day 29, Day 36, Day 43, Day 50, Day 57, Day 64, Day 71, Day 78 (pre-dose and 1 hour, 2 hours, and 6 hours post-dose), Day 79, Day 85, Day 92, Day 106, Day 134, Day 162 (to be performed pre-dose on Day 8 to Day 78)
- 6) Blood tests and urinalysis
  - <Observation point>

Day 1,\*10 Day 2, Day 22, Day 50, Day 78,\*10 Day 85, Day 106, Day 134, Day 162 (to be performed pre-dose on Day 1 to Day 78)

7) 12-lead electrocardiogram

<Observation point>

See 6.2

8) MRI or CT

<Location of imaging>

Upper arm: MRI or CT (to confirm the location of muscle biopsy)

Thigh: MRI

<Investigation point>

To be performed once in the period from Day 85 to Day 99.

## 9) Muscle biopsy

<Investigation point>

To be performed once in the period from Day 85 to Day 99. To be performed after MRI or CT, motor function assessment, respiratory function assessment, cardiac function assessment, and quantitative muscle strength assessment.

## 10) Motor function assessment

<Investigation point>

To be performed twice in the period from Day 85 to Day 99.

## 11) Respiratory function assessment

<Investigation point>

To be performed once in the period from Day 85 to Day 99.

#### 12) Cardiac function assessment

<Investigation point>

To be performed once in the period from Day 85 to Day 99.

## 13) Quantitative muscle strength assessment

<Investigation point>

To be performed twice in the period from Day 85 to Day 99.

#### 14) Blood collection

Pharmacokinetics

<Blood collection point>

See 6.7

Anti-dystrophin antibody

<Blood collection point>

Day 85

• Anti-DS-5141b antibody

<Blood collection point>

Day 85

Blood cell dystrophin mRNA

<Blood collection point>

Day 85

#### 15) Urine collection

Urine protein

<Urine collection point>

Day 85

\*10: 24-hour urine pooling will be performed, starting on the previous day.

#### 6.4.4 Part 2-Extension

# 6.4.4.1 Items to Be Performed Before the First Dose of Study Drug in Part 2-Extension

If subjects who have finished Part 2 continue to participate, the following will be performed from 14 days before the first dose of the study drug up to the day before the first dose of the study drug (Day 0). For subjects participating from Part 2-Extension, "6.4.1 Items to Be Performed After Registration up to the Day Before the First Dose of Study Drug (Day 0)" will be performed, and these tests will not be necessary.

- 1) Day of informed consent (or confirmation of intent) by the subject for participation in Part 2-Extension
- 2) Day of informed consent by the legally acceptable representative for participation in Part 2-Extension
- 3) Checking concomitant medications and concomitant therapy
- 4) Height and body weight
- 5) Vital signs and clinical findings
- 6) Blood tests and urinalysis
- 7) 12-lead electrocardiogram
- 8) MRI (only for subjects in whom MRI can be performed appropriately) <Location of imaging>

MRI: Thigh

- 9) Motor function assessment\*11
- 10) Respiratory function assessment
- 11) Cardiac function assessment
- 12) Quantitative muscle strength assessment\*11
- 13) Blood collection
  - Anti-dystrophin antibody
- 14) Urine collection
  - Urine protein

\*11: To be performed twice.

# 6.4.4.2 Items to Be Performed During the Treatment Period (Week 1/ Day 1 to Week 48/ Day 336) and Follow-Up Period (Week 49/ Day 337 to Week 52/ Day 358)

The visit window for items performed on Week 2/ Day 8 to Week 50/ Day 344 is  $\pm 2$  days, and the visit window for items performed on Week 52/ Day 358 is  $\pm 7$  days.

- Administration status of the study drug
   Whether the study drug was administered, date/time of study drug administration,
   dose level, actual dose (mg)
- 2) Investigating concomitant medications and concomitant therapy
- 3) Investigating adverse events
- 4) Height and body weight <Observation point>
  Week 13/ Day 85, Week 25/ Day 169, Week 37/ Day 253, Week 48/ Day 330
- 5) Vital signs and clinical findings
  - <Observation point>

Week 1/ Day 1 (pre-dose and 4 hours post-dose), Week 1/ Day 2, Week 2/ Day 8, Week 3/ Day 15, Week 4/ Day 22, Week 5/ Day 29, Week 6/ Day 36, Week 7/ Day 43, Week 8/ Day 50, Week 9/ Day 57, Week 10/ Day 64, Week 11/ Day 71, Week 12/ Day 78, Week 13/ Day 85 (pre-dose and 4 hours post-dose), Week 14/ Day 92, Week 15/ Day 99, Week 16/ Day 106, Week 17/ Day 113, Week 18/ Day 120, Week 19/ Day 127, Week 20/ Day 134, Week 21/ Day 141, Week 22/ Day 148, Week 23/ Day 155, Week 24/ Day 162, Week 25/ Day 169 (pre-dose and 4 hours post-dose), Week 26/ Day 176, Week 27/ Day 183, Week 28/ Day 190, Week 29/ Day 197, Week 30/ Day 204, Week 31/ Day 211, Week 32/ Day 218, Week 33/ Day 225, Week 34/ Day 232, Week 35/ Day 239, Week 36/ Day 246, Week 37/ Day 253 (pre-dose and 4 hours post-dose), Week 38/ Day 260, Week 39/ Day 267, Week 40/ Day 274, Week 41/ Day 281, Week 42/ Day 288, Week 43/ Day 295, Week 44/ Day 302, Week 45/ Day 309, Week 46/ Day 316, Week 47/ Day 323, Week 48/ Day 330 (pre-dose and 4 hours post-dose), Week 48/ Day 331, Week 49/ Day 337, Week 52/ Day 358 (to be performed pre-dose from Week 2/ Day 8 to Week 12/ Day 78, from Week 14/ Day 92 to Week 24/ Day 162, from Week 26/ Day 176 to Week 36/ Day 246, and from Week 38/ Day 260 to Week 47/ Day 323)

#### 6) Blood tests

<Observation point>

Week 1/ Day 1, Week 1/ Day 2, Week 5/ Day 29, Week 9/ Day 57, Week 13/ Day 85, Week 17/ Day 113, Week 21/ Day 141, Week 25/ Day 169, Week 29/ Day 197, Week 33/ Day 225, Week 37/ Day 253, Week 41/ Day 281, Week 45/ Day 309, Week 48/ Day 330, Week 49/ Day 337, Week 52/ Day 358 (to be performed pre-dose on Week 1/ Day 1 and from Week 5/ Day 29 to Week 48/ Day 330)

# 7) Urinalysis

<Observation point>

Week 1/ Day 1 (pre-dose,\*12 from 4 hours post-dose), Week 1/ Day 2, Week 5/ Day 29, Week 9/ Day 57, Week 13/ Day 85 (pre-dose,\*12 from 4 hours post-dose), Week 17/ Day 113, Week 21/ Day 141, Week 25/ Day 169 (pre-dose,\*12 from 4 hours post-dose), Week 29/ Day 197, Week 33/ Day 225, Week 37/ Day 253 (pre-dose,\*12 from 4 hours post-dose), Week 41/ Day 281, Week 45/ Day 309, Week 48/ Day 330 (pre-dose,\*12 from 4 hours post-dose), Week 49/ Day 337, Week 52/ Day 358 (to be performed pre-dose on Week 5/ Day 29, Week 9/ Day 57, Week 17/ Day 113, Week 21/ Day 141, Week 29/ Day 197, Week 33/ Day 225, Week 41/ Day 281, Week 45/ Day 309)

#### 8) 12-lead electrocardiogram

<Observation point>

See 6.2

#### 9) MRI

<Location of imaging>

Upper arm: MRI or CT (to confirm the location of muscle biopsy)

Thigh: MRI

<Investigation point>

To be performed once in the period from Week 49/ Day 337 to Week 51/ Day 351.

# 10) Muscle biopsy

<Investigation point>

To be performed once in the period from Week 49/ Day 337 to Week 51/ Day 351. To be performed after MRI or CT, motor function assessment, respiratory function assessment, cardiac function assessment, and quantitative muscle strength assessment.

#### 11) Motor function assessment

<Investigation point>

To be performed once each in the period from Week 12/ Day 84 to

Week 13/ Day 85 (pre-dose), the period from Week 24/ Day 168 to

Week 25/ Day 169 (pre-dose), and the period from Week 36/ Day 252 to

Week 37/ Day 253 (pre-dose), and twice in the period from Week 49/ Day 337 to

Week 51/ Day 351.

# 12) Respiratory function assessment

<Investigation point>

To be performed once each in the period from Week 12/ Day 84 to

Week 13/ Day 85 (pre-dose), the period from Week 24/ Day 168 to

Week 25/ Day 169 (pre-dose), the period from Week 36/ Day 252 to

Week 37/ Day 253 (pre-dose), and the period from Week 49/ Day 337 to

Week 51/ Day 351.

## 13) Cardiac function assessment

<Investigation point>

To be performed once each in the period from Week 12/ Day 84 to

Week 13/ Day 85 (pre-dose), the period from Week 24/ Day 168 to

Week 25/ Day 169 (pre-dose), the period from Week 36/ Day 252 to

Week 37/ Day 253 (pre-dose), and the period from Week 49/ Day 337 to

Week 51/ Day 351.

#### 14) Quantitative muscle strength assessment

<Investigation point>

To be performed once each in the period from Week 12/ Day 84 to

Week 13/ Day 85 (pre-dose), the period from Week 24/ Day 168 to

Week 25/ Day 169 (pre-dose), and the period from Week 36/ Day 252 to

Week 37/ Day 253 (pre-dose), and performed twice in the period from

Week 49/ Day 337 to Week 51/ Day 351.

# 15) Blood collection

Pharmacokinetics

<Blood collection point>

See 6.7

Anti-dystrophin antibody

<Blood collection point>

Week 49/ Day 337

Anti-DS-5141b antibody
 <Blood collection point>
 Week 49/ Day 337

#### 16) Urine collection

Urine protein
 <Urine collection point>
 Week 13/ Day 85, Week 25/ Day 169, Week 37/ Day 253, Week 49/ Day 337

#### 6.4.5 Part 2-Extension-2

# 6.4.5.1 Items to Be Performed Before the First Dose of Study Drug in Part 2-Extension-2

If subjects who have finished Part 2-Extension continue to participate, the following will be performed from 14 days before the first dose of the study drug up to the day before the first dose of the study drug (Day 0). For subjects participating from Part 2-Extension-2, "6.4.1 Items to Be Performed After Registration up to the Day Before the First Dose of Study Drug (Day 0)" will be performed, and these tests will not be necessary.

- 1) Day of informed consent (or confirmation of intent) by the subject for participation in Part 2-Extension-2
- 2) Day of informed consent by the legally acceptable representative for participation in Part 2-Extension-2
- 3) Checking concomitant medications and concomitant therapy
- 4) Height and body weight
- 5) Vital signs and clinical findings
- 6) Blood tests and urinalysis
- 7) 12-lead electrocardiogram
- 8) CCI
- 9) MRI (only for subjects in whom MRI can be performed appropriately) <Location of imaging>

MRI: Thigh

- 10) Motor function assessment\*13
- 11) Respiratory function assessment
- 12) Cardiac function assessment

\*12: 24-hour urine pooling will be performed, starting on the previous day.

- 13) Quantitative muscle strength assessment\*13
- 14) Blood collection
  - Anti-dystrophin antibody
- 15) Urine collection
  - Urine protein

# 6.4.5.2 Items to Be Performed During the Treatment Period (Week 1/ Day 1 to Week 48/ Day 336) and Follow-Up Period (Week 49/ Day 337 to Week 52/ Day 358)

The visit window for items performed on Week 2/ Day 8 to Week 50/ Day 344 is ±2 days, and the visit window for items performed on Week 52/ Day 358 is ±7 days. Subjects who complete 48 weeks of study drug administration in Part 2-Extension-2 and complete efficacy assessment after administration may participate in the long-term extension study. For subjects who participate in the long-term extension study, Week 52/ Day 358 will not be performed.

As a measure to prevent the spread of the novel coronavirus, self-administration will be allowed. Consent for self-administration will be obtained from the legally acceptable representative, and the guardian performing self-administration will be given training in the method of storing the study drug and the method of administering the study drug before self-administration starts.

- 1) Administration status of the study drug
  - Whether the study drug was administered, date/time of study drug administration, dose level, actual dose (mg), and checking the "Self-Injection Diary" if self-administration was performed
  - <Time points at which self-administration is possible>
  - Week 28/ Day 190, Week 30/ Day 204, Week 31/ Day 211, Week 32/ Day 218,
  - Week 34/ Day 232, Week 35/ Day 239, Week 36/ Day 246, Week 38/ Day 260,
  - Week 39/ Day 267, Week 40/ Day 274, Week 42/ Day 288, Week 43/ Day 295,
  - Week 44/ Day 302, Week 46/ Day 316, Week 47/ Day 323
- 2) Investigating concomitant medications and concomitant therapy
- 3) Investigating adverse events
- 4) Height and body weight
  - <Observation point>

\*13: To be performed twice.

Week 13/ Day 85, Week 25/ Day 169, Week 37/ Day 253, Week 48/ Day 330

## 5) Vital signs and clinical findings

If self-injection is performed, vital signs will be measured to the extent possible. Clinical findings will be checked by a method such as making a telephone call. <Observation point>

Week 1/ Day 1 (pre-dose and 4 hours post-dose), Week 1/ Day 2, Week 2/ Day 8 (pre-dose and 4 hours post-dose), Week 3/ Day 15 (pre-dose and 4 hours post-dose), Week 4/ Day 22 (pre-dose and 4 hours post-dose), Week 5/ Day 29, Week 6/ Day 36, Week 7/ Day 43, Week 8/ Day 50, Week 9/ Day 57, Week 10/ Day 64, Week 11/ Day 71, Week 12/ Day 78, Week 13/ Day 85 (pre-dose and 4 hours post-dose), Week 14/ Day 92, Week 15/ Day 99, Week 16/ Day 106, Week 17/ Day 113, Week 18/ Day 120, Week 19/ Day 127, Week 20/ Day 134, Week 21/ Day 141, Week 22/ Day 148, Week 23/ Day 155, Week 24/ Day 162, Week 25/ Day 169 (pre-dose and 4 hours post-dose), Week 26/ Day 176, Week 27/ Day 183, Week 28/ Day 190, Week 29/ Day 197, Week 30/ Day 204, Week 31/ Day 211, Week 32/ Day 218, Week 33/ Day 225, Week 34/ Day 232, Week 35/ Day 239, Week 36/ Day 246, Week 37/ Day 253 (pre-dose and 4 hours post-dose), Week 38/ Day 260, Week 39/ Day 267, Week 40/ Day 274, Week 41/ Day 281, Week 42/ Day 288, Week 43/ Day 295, Week 44/ Day 302, Week 45/ Day 309, Week 46/ Day 316, Week 47/ Day 323, Week 48/ Day 330 (pre-dose and 4 hours post-dose), Week 48/ Day 331, Week 49/ Day 337, Week 52/ Day 358 (to be performed pre-dose on Week 2/ Day 8 to Week 12/ Day 78, Week 14/ Day 92 to Week 24/ Day 162, Week 26/ Day 176 to Week 36/ Day 246, and Week 38/ Day 260 to Week 47/ Day 323)

#### 6) Blood tests

<Observation point>

Week 1/ Day 1, Week 1/ Day 2, Week 5/ Day 29, Week 9/ Day 57, Week 13/ Day 85, Week 17/ Day 113, Week 21/ Day 141, Week 25/ Day 169, Week 29/ Day 197, Week 33/ Day 225, Week 37/ Day 253, Week 41/ Day 281, Week 45/ Day 309, Week 48/ Day 330, Week 49/ Day 337, Week 52/ Day 358 (to be performed pre-dose on Week 1/ Day 1 and Week 5/ Day 29 to Week 48/ Day 330)

## 7) Urinalysis

<Observation point>

Week 1/ Day 1 (pre-dose, \*14 from 4 hours post-dose), Week 1/ Day 2,

Week 5/ Day 29, Week 9/ Day 57, Week 13/ Day 85 (pre-dose,\*14 from 4 hours post-dose), Week 17/ Day 113, Week 21/ Day 141, Week 25/ Day 169 (pre-dose,\*14 from 4 hours post-dose), Week 29/ Day 197, Week 33/ Day 225, Week 37/ Day 253 (pre-dose,\*14 from 4 hours post-dose), Week 41/ Day 281, Week 45/ Day 309, Week 48/ Day 330 (pre-dose,\*14 from 4 hours post-dose), Week 49/ Day 337, Week 52/ Day 358 (to be performed pre-dose on Week 5/ Day 29, Week 9/ Day 57, Week 17/ Day 113, Week 21/ Day 141, Week 29/ Day 197, Week 33/ Day 225, Week 41/ Day 281, Week 45/ Day 309)

8) 12-lead electrocardiogram

<Observation point>

See 6.2

# 9) CCI

<Investigation point>

To be performed once each in the period from Week 4/ Day 22 to Week 6/ Day 36 and the period from Week 49/ Day 337 to Week 51/ Day 351.

#### 10) MRI

<Location of imaging>

Upper arm: MRI or CT (to confirm the location of muscle biopsy)

Thigh: MRI

<Investigation point>

To be performed once in the period from Week 49/ Day 337 to Week 51/ Day 351.

## 11) Muscle biopsy

<Investigation point>

To be performed once in the period from Week 49/ Day 337 to Week 51/ Day 351. To be performed after MRI or CT, motor function assessment, respiratory function assessment, cardiac function assessment, and quantitative muscle strength assessment.

#### 12) Motor function assessment (lower limbs)

<Investigation point>

To be performed once each in the period from Week 12/ Day 84 to Week 13/ Day 85 (pre-dose), the period from Week 24/ Day 168 to Week 25/ Day 169 (pre-dose), and the period from Week 36/ Day 252 to Week 37/ Day 253 (pre-dose), and performed twice in the period from Week 49/ Day 337 to Week 51/ Day 351.

#### 13) Motor function assessment (upper limbs)

<Investigation point>

To be performed once each in the period from Week 24/ Day 168 to

Week 25/ Day 169 (pre-dose) and the period from Week 36/ Day 252 to

Week 37/ Day 253 (pre-dose), and performed twice in the period from

Week 49/ Day 337 to Week 51/ Day 351. Note that measurement will be started when possible, at a timing that suits the subject's schedule.

#### 14) Respiratory function assessment

<Investigation point>

To be performed once each in the period from Week 12/ Day 84 to

Week 13/ Day 85 (pre-dose), the period from Week 24/ Day 168 to

Week 25/ Day 169 (pre-dose), the period from Week 36/ Day 252 to

Week 37/ Day 253 (pre-dose), and the period from Week 49/ Day 337 to

Week 51/ Day 351.

## 15) Cardiac function assessment

<Investigation point>

To be performed once each in the period from Week 12/ Day 84 to

Week 13/ Day 85 (pre-dose), the period from Week 24/ Day 168 to

Week 25/ Day 169 (pre-dose), the period from Week 36/ Day 252 to

Week 37/ Day 253 (pre-dose), and the period from Week 49/ Day 337 to

Week 51/ Day 351.

#### 16) Quantitative muscle strength assessment

<Investigation point>

To be performed once each in the period from Week 12/ Day 84 to

Week 13/ Day 85 (pre-dose), the period from Week 24/ Day 168 to

Week 25/ Day 169 (pre-dose), and the period from Week 36/ Day 252 to

Week 37/ Day 253 (pre-dose), and performed twice in the period from

Week 49/ Day 337 to Week 51/ Day 351.

# 17) Blood collection

Pharmacokinetics

<Blood collection point>

See 6.7

Anti-dystrophin antibody

<Blood collection point>

Week 49/ Day 337

Anti-DS-5141b antibody
 Blood collection point>
 Week 49/ Day 337

- 18) Urine collection
  - Urine protein

<Urine collection point>

Week 13/ Day 85, Week 25/ Day 169, Week 37/ Day 253, Week 49/ Day 337

19) Whether the subject can participate in the long-term extension study <Timing of confirmation>
Week 49/ Day 337 to Week 51/ Day 351 (An explanation of the long-term extension study may be provided to subjects who complete 48 weeks of study drug administration in Part 2-Extension-2.)

\*14: 24-hour urine pooling will be performed, starting on the previous day.

#### 6.5 Test Items on Withdrawal from the Study and their Timing

Within 7 days from the date when the investigator or subinvestigator decides that the subject should be withdrawn from the study, the following investigations, examinations, and tests will be performed, as far as possible.

# 6.5.1 For Withdrawal in the Period from Day 1 to Day 15 of Any Dose Level in Part 1

- 1) Investigating concomitant medications and concomitant therapy
- 2) Investigating adverse events
- 3) Body weight
- 4) Vital signs and clinical findings
- 5) Blood tests and urinalysis
- 6) 12-lead electrocardiogram
- 7) Blood collection
  - Pharmacokinetics
  - Anti-dystrophin antibody
  - Anti-DS-5141b antibody
  - Blood cell dystrophin mRNA
- 8) Urine collection
  - Urine protein

Urine DS-5141b metabolites

# 6.5.2 For Withdrawal in the Period from Day 1 to Day 85 of Part 2

- 1) Investigating concomitant medications and concomitant therapy
- 2) Investigating adverse events
- 3) Body weight
- 4) Vital signs and clinical findings
- 5) Blood tests and urinalysis
- 6) 12-lead electrocardiogram
- 7) MRI or CT

<Location of imaging>

Upper arm: MRI or CT (to confirm the location of muscle biopsy)

Thigh: MRI

- 8) Muscle biopsy
- 9) Motor function assessment
- 10) Respiratory function assessment
- 11) Cardiac function assessment
- 12) Quantitative muscle strength assessment
- 13) Blood collection
  - Pharmacokinetics
  - Anti-dystrophin antibody
  - Anti-DS-5141b antibody
  - Blood cell dystrophin mRNA
- 14) Urine collection
  - Urine protein

# 6.5.3 For Withdrawal in the Period from Week 1/ Day 1 to Week 49/ Day 337 of Part 2-Extension or from Week 1/ Day 1 to Week 49/ Day 337 of Part 2-Extension-2

- 1) Investigating concomitant medications and concomitant therapy
- 2) Investigating adverse events
- 3) Height and body weight
- 4) Vital signs and clinical findings
- 5) Blood tests
- 6) Urinalysis

- 7) 12-lead electrocardiogram
- 8) CCI \*15
- 9) MRI or CT

<Location of imaging>

Upper arm: MRI or CT (to confirm the location of muscle biopsy)

Thigh: MRI

- 10) Muscle biopsy
- 11) Motor function assessment (lower limbs and upper limbs)\*16
- 12) Respiratory function assessment
- 13) Cardiac function assessment
- 14) Quantitative muscle strength assessment
- 15) Blood collection
  - Pharmacokinetics
  - Anti-dystrophin antibody
  - Anti-DS-5141b antibody
- 16) Urine collection
  - Urine protein
- \*15: To be performed if the subject is withdrawn in the period from Week 1/ Day 1 to Week 49/ Day 337 of Part 2-Extension-2.
- \*16: Not necessary if motor function assessment (upper limbs) was not performed even once in the period from Week 24/ Day 168 to Week 37/ Day 253 (pre-dose) of Part 2-Extension-2.
- 6.5.4 For Withdrawal in the Period from Day 16 to Day 64 of Part 1, from Day 86 to Day 162 of Part 2, from Week 49/ Day 338 to Week 52/ Day 358 of Part 2-Extension, or from Week 49/ Day 338 to Week 52/ Day 358 of Part 2-Extension-2
- 1) Investigating concomitant medications and concomitant therapy
- 2) Investigating adverse events
- 3) Height and body weight
- 4) Vital signs and clinical findings
- 5) Blood tests and urinalysis
- 6) 12-lead electrocardiogram
- 7) (CC) \*17

8) MRI or  $CT^{*18}$ 

<Location of imaging>

Upper arm: MRI or CT (to confirm the location of muscle biopsy)

Thigh: MRI

- 9) Muscle biopsy\*18
- 10) Motor function assessment (lower limbs and upper limbs)\*18, 19
- 11) Respiratory function assessment\*18
- 12) Cardiac function assessment\*18
- 13) Quantitative muscle strength assessment\*18
- \*17: To be performed for subjects who participated in Part 2-Extension-2, but not necessary if performed on Week 49/ Day 337 of Part 2-Extension-2 in subjects withdrawn in the period from Week 49/ Day 338 to Week 52/ Day 358 of Part 2-Extension-2.
- \*18: Not necessary in subjects withdrawn in the period from Day 86 to Day 162 of Part 2 if performed on Day 85 of Part 2. Not necessary for subjects withdrawn in the period from Week 49/ Day 338 to Week 52/ Day 358 of Part 2-Extension if performed on Week 49/ Day 337 of Part 2-Extension, and not necessary for subjects withdrawn in the period from Week 49/ Day 338 to Week 52/ Day 358 of Part 2-Extension-2 if performed on Week 49/ Day 337 of Part 2-Extension-2.
- \*19: Not necessary if motor function assessment (upper limbs) was not performed even once in the period from Week 24/ Day 168 to Week 37/ Day 253 (pre-dose) of Part 2-Extension-2.

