# 6.4.2.2 Items to Be Performed During the Treatment Period (Day 1 to Day 14) and Follow-Up Period (Day 15 to Day 64) for Each Dose Level

The visit window for items performed on Day 15 and Day 22 is  $\pm 2$  days, and the visit window for items performed on Day 36 and Day 64 is  $\pm 7$  days.

- Checking the administration status of the study drug Whether the study drug was administered, date/time of study drug administration, dose level, actual dose (mg)
- 2) Investigating concomitant medications and concomitant therapy
- 3) Investigating adverse events
- 4) Body weight
  - <Observation point>

Day 15

- 5) Vital signs and clinical findings
  - <Observation point>

Day 1 (pre-dose and 1 hour, 2 hours, and 6 hours post-dose), Day 2, Day 4, Day 8 (pre-dose and 1 hour, 2 hours, and 6 hours post-dose), Day 9, Day 11, Day 15, Day 22, Day 36, Day 64

6) Blood tests and urinalysis

<Observation point>

Day 1 (pre-dose),\*8 Day 2, Day 4,\*8 Day 8 (pre-dose), Day 9, Day 11,\*8 Day 15, Day 36, Day 64

- 7) 12-lead electrocardiogram
  - <Observation point>

See 6.2

- 8) Blood collection
  - Pharmacokinetics

<Blood collection point>

See 6.7

- Anti-dystrophin antibody
  - <Blood collection point>

Day 15

- Anti-DS-5141b antibody
  - <Blood collection point>

Day 15

Blood cell dystrophin mRNA

<Blood collection point> Day 15

- 9) Urine collection
  - Urine protein

<Urine collection point>

Day 15

• Urine DS-5141b metabolites

<Urine collection point>

Day 9

#### 6.4.3 Part 2

## 6.4.3.1 Items to Be Performed Before the First Dose of Study Drug in Part 2

If subjects who have finished Part 1 continue to participate, the following will be performed from 14 days before the first dose of the study drug up to the day before the first dose of the study drug (Day 0). For subjects participating from Part 2, "6.4.1 Items to Be Performed After Registration up to the Day Before the First Dose of Study Drug (Day 0)" will be performed, and these tests will not be necessary.

- 1) Checking concomitant medications and concomitant therapy
- 2) Height and body weight
- 3) Vital signs and clinical findings
- 4) Blood tests and urinalysis
- 5) 12-lead electrocardiogram
- 6) MRI (only for subjects in whom MRI can be performed appropriately)

<Location of imaging>

MRI: Thigh

- 7) Motor function assessment\*9
- 8) Respiratory function assessment
- 9) Cardiac function assessment
- 10) Quantitative muscle strength assessment\*9
- 11) Blood collection

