# 6.9 Expression of Dystrophin Protein and Production of Exon 45-Skipped Dystrophin mRNA in Muscle Tissue (Muscle Biopsy)

To measure the dystrophin protein in muscle tissue and the dystrophin mRNA induced by exon 45 skipping, after registration, before the first dose of the study drug in each subject, after the last dose of the study drug (Day 85 to Day 99, or at withdrawal) in Part 2, after the last dose of the study drug (Week 49/ Day 337 to Week 51/ Day 351, or at withdrawal) in Part 2-Extension, and after the last dose of the study drug (Week 49/ Day 337 to Week 51/ Day 351, or at withdrawal) in Part 2-Extension-2, muscle tissue will be collected from, in principle, the biceps brachii muscle by open muscle biopsy. The location of collection will be decided after checking the condition of the muscle by MRI or CT performed in advance. After collection, the

specimen will be processed promptly, and stored frozen (set temperature:  $\leq -70^{\circ}$ C) in a container prepared by the sponsor or central laboratory until it is submitted to the clinical specimen storage facility contracted by the sponsor. Details are specified in a separate procedure.

The investigator or subinvestigator will record whether a muscle biopsy was performed, the date of biopsy, and the region of the collected muscle on the case report form.

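### Section 6.5.4 lists an open muscle biopsy for a boy who withdraws on Day 16 to 64 of Part 1, while 6.5.1, 6.4.2.2 and 6.9 plan no post-dose biopsy in that part

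*Combined protocol and SAP*

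**What the plan says.** **Section 6.5.4.** The heading opens "For Withdrawal in the Period from Day 16 to Day 64 of Part 1" and continues with the follow-up periods of Part 2, Part 2-Extension and Part 2-Extension-2. All four periods share one list, which includes "9) Muscle biopsy". Item 8 (imaging, including an upper-arm image to locate the biopsy), item 9 and items 10 to 13 (motor, respiratory, cardiac and strength tests) all carry footnote *18.

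**Footnote *18.** It begins "Not necessary in subjects withdrawn in the period from Day 86 to Day 162 of Part 2 if performed on Day 85" of that part, then gives matching waivers for the two extensions. Part 1 is not mentioned.

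**Section 6.5.1.** Headed "For Withdrawal in the Period from Day 1 to Day 15 of Any Dose Level in Part 1", it has eight items. None is a biopsy, an image or a function test.

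**Section 6.4.2.2.** The Part 1 schedule, covering "Treatment Period (Day 1 to Day 14) and Follow-Up Period (Day 15 to Day 64) for Each Dose Level", contains no biopsy.

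**Section 6.9.** Every subject has an open biopsy, in principle of the biceps, before his first dose. Post-dose biopsies follow "after the last dose of the study drug (Day 85 to Day 99, or at withdrawal) in Part 2", and on the same pattern in each extension. No post-dose or withdrawal biopsy is named for Part 1.

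**Section 6.5, opening.** The withdrawal "examinations, and tests will be performed, as far as possible".

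**The concern.** On a literal reading, a boy who leaves Part 1 on Day 15 is not listed for a biopsy and the same boy leaving on Day 16 is. No reason is given for the change. A Part 1 entrant has already had one open biopsy before dosing, so this would be his second, after only the two scheduled doses of a dose level.

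The procedure is surgical and the subjects are children, so its place in the protocol should be unambiguous. It is also unclear what the sample would be for: the efficacy listings have no column for it.

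**Working it through.** No formula or stated figure is involved. The check sets the sections side by side.

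1. **Does 6.5.4 reach Part 1?** Yes. Day 16 to 64 of Part 1 is the first period in its heading, and the list is not split by part.

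2. **Does footnote *18 remove the biopsy for Part 1?** No. It has three waivers (Part 2, Part 2-Extension, Part 2-Extension-2), each conditional on the test having been done at a stated visit of that part. A Part 1 withdrawal meets none of them.

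3. **Do other sections plan a post-dose biopsy in Part 1?**

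| Section | Subject | Post-dose or withdrawal biopsy in Part 1 |
|---|---|---|
| 6.5.4 | Withdrawal, Day 16 to 64 | Yes |
| 6.5.1 | Withdrawal, Day 1 to 15 | No |
| 6.4.2.2 | Part 1 schedule, Day 1 to 64 | No |
| 6.9 | Biopsy timing | No |

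One section lists it and three do not.

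4. **Does the protocol elsewhere name Part 1 when it wants a withdrawal sample there?** Yes. For anti-dystrophin antibody (6.10), anti-DS-5141b antibody (6.11), blood-cell dystrophin mRNA (6.12.3) and urine protein (6.12.5), the Part 1 time point is Day 15 or withdrawal. Section 6.9 has no such wording. In addition, the rationale in Section 3 links the 12-week length of Part 2 to confirming dystrophin expression, and sets the Part 1 duration by nonclinical safety coverage. Both facts fit a pooled list whose footnote overlooked Part 1, but neither proves it.

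5. **Would the analysis display the sample?** Sections 11.4.2.1 and 11.4.2.2 name three time points: before the first dose, end of Part 2, and end of Part 2-Extension-2. A Part 1 withdrawal biopsy fits 0 of the 3.

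6. **Exposure at that point.** At Dose Level 1 the two doses come to 2 × 0.1 = 0.2 mg/kg. This is the smallest cumulative dose after which 6.5.4 would list the biopsy, assuming both scheduled doses were given.

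7. **Function tests, items 10 to 13.** These stand differently. Section 10 describes duplicate motor and strength testing (items 1 and 4) in a sentence that includes Part 1 among the parts assessed after the last dose. Yet the opening sentences of the same items give only a pre-dose assessment in Part 1, and 6.4.2.2 schedules none after dosing. Section 10 is therefore itself unclear about Part 1.

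**The case against.** The strongest reply is that hardly anyone can be affected. Section 1.2.6 reports Part 2 complete by 19 Mar 2018, and the 2.0 and 6.0 mg/kg doses that Part 1 was to inform have been chosen and given. Section 5.8 still allows a subject to be added to Part 1, but the documents give no reason to expect it. The tests are also best effort, and 4.3 makes them depend on the cooperation of the subject and his representative. All of this stands and limits the size of the point. It does not remove the item from the list.

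A reader might infer more than the text supports:

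- **That Part 1 has no biopsy at all.** Section 6.9 requires one before the first dose in every subject, including Part 1 entrants. Only a post-dose biopsy is unplanned.
- **That no analysis could use the result.** The exposure-response modelling in 11.4.3 covers biomarkers and efficacy indicators without restricting time points. Under 11.2.1 the result would also count as post-dose efficacy data, so the third exclusion would not apply, and the boy could enter the efficacy population with a value that no listing shows.
- **That items 8 to 13 could all be dropped without losing planned data.** Sections 11.4.5.1 to 11.4.5.4 summarise the function tests by time point, with change from before the first dose. The argument from the biopsy listings does not carry over to them.

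Appendix 3, the schedule of examinations, is not reproduced in the text available, so whether it repeats 6.5.4 could not be checked.

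**Conclusion.** The inconsistency is real and the point is minor. Section 6.5.4 with footnote *18 lists a post-dose open biopsy and its siting image for withdrawal on Day 16 to 64 of Part 1. Sections 6.5.1, 6.4.2.2 and 6.9 do not plan one, and the primary and secondary listings have no place for it.

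The live effect is limited to a subject newly added to Part 1. That rests on reading the reported completion of Part 2 as meaning that Part 1 has also ended. The documents do not show that any boy had such a biopsy, nor do they settle whether it was intended. The conclusion is only that the sections cannot all stand as written.

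**What to change.** Reconcile 6.5.4 and footnote *18 with 6.5.1, 6.4.2.2 and 6.9 on the Part 1 biopsy and the upper-arm image that sites it. There are two ways:

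- If the biopsy is not intended, add a sentence to *18 excluding Part 1 withdrawals from item 9 and from the upper-arm image in item 8.
- If it is intended, add the time point to 6.9 and to the listings in 11.4.2.1 and 11.4.2.2, and say why it starts at Day 16.

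Separately, state whether the function tests in items 10 to 13 apply to Part 1 withdrawals, and align Section 10 items 1 and 4 with 6.4.2.2 on whether Part 1 has a post-dose assessment. Check Appendix 3 at the same time.

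The cost is one sentence under the first option and a few lines under the second. The first option removes no sample named in the efficacy listings, but it does give up a possible input to the exploratory modelling.
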